b. Specific Aim/Hypothesis

Aim 1: Examine the immediate post-intervention effect of CHAMP (compared to control participants) on MC, PMC, and PA in preschool-age children.

Hypothesis 1: Children in CHAMP, compared to control, will demonstrate higher levels of MC, PMC and PA at post-intervention.

Aim 2: Assess the sustainable effect of CHAMP (compared to control participants) on MC, PMC, and PA across middle childhood.

Hypothesis 2: Children in CHAMP, compared to control, will demonstrate higher levels of MC, PMC and daily PA across the 3 yr follow-up (middle childhood) period (sustainable).

Aim 3: Examine and compare the immediate and long-term mediating effect of PMC on the relationship between MC and PA in preschool-age children in the CHAMP and control.

Hypothesis 3: PMC will not mediate the relationship between MC and PA at baseline. PMC will mediate the relationship between MC and PA immediately post intervention and across the 3-yr follow-up period.

Impact. Positive findings will support the development of early childhood motor competence and physical activity programs that promote positive and sustainable physical activity behaviors that contribute to healthy growth and development.

B. Objective 2. Cohort 2 participants will not partake in Objective 2.

A secondary aim of the project (i.e., funded NIH supplement - FOA PA-16-334, *Science of Behavior Change*) is to examine the immediate (pre- to post-test) effects of the CHAMP intervention on SR, and associations between SR and changes in motor competence, perceived motor competence, and PA. SR will be assayed using a multi-method approach, including direct assessment of child behavioral and attentional regulation, computer-based assessment of cognitive control strategies, and teacher-reported emotional regulation.

The specific aims for this Supplement will be tested in 120 preschool-aged children (3.5-5 years) who are attending Head Start and receiving CHAMP (n = 10 classrooms) or an active free-play/recess control condition (n = 10 classrooms).

b. Specific Aim/Hypothesis

Aim 1. Test the hypothesis that CHAMP improves child SR (*cognitive flexibility, working memory, behavioral inhibition, emotion regulation*) from pre- to post-test, compared to control.

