The immediate post-intervention effect of CHAMP (compared to control participants) on each SR outcome variable will be evaluated at post-intervention (month 9). We will examine descriptive statistics for both pre- and post-intervention SR measures of the outcome variables for each group. The change in *cognitive flexibility, working memory, behavioral inhibition, and emotion regulation* scores will be compared between the intervention (CHAMP) and control groups using regression models, adjusting for other confounding factors. Random effects will be included in the model to accommodate for the potential within-cluster correlations due to nested classroom data. We anticipate that some children will have only partial adherence to the intervention (i.e. attend a subset of sessions), thus we will also conduct a dose-response analysis where dose corresponds to number of sessions. We will also investigate the amount of attrition from pre- to post-intervention, and attempt to identify baseline (or pre-intervention) predictors of the likelihood of dropping out (as an indication of possible bias in the change estimates).

Aim 2. Test the hypothesis that improvement in child SR indicators (*cognitive flexibility, working memory, behavioral inhibition, and emotion regulation*) is associated with improved motor competence, perceived motor competence, and objectively-measured PA from pre- to post-test.

We will examine strength of association between each SR variable and our outcomes of interest using bivariate analyses to compare change in SR to change in motor competence, perceived motor competence, and PA (using an alpha value of $p < .05$). We will also use multivariate regression models (controlling for covariates as needed) to examine the association of SR and outcomes in each group (CHAMP and control) in order to test whether the strength of association varies by intervention status.

Sample Size, Power Analysis and Sample Attrition. The sample size was calculated based on our findings from preliminary data. After 9 months, we will be able to detect effects between intervention and control groups with 85% power at an alpha level of 0.05, with a total of 98 subjects (49 subjects per arm). To account for a total of a 16.5% loss at post-intervention, we will recruit 120 subjects (60 subjects per arm) at baseline.

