Overall Analysis Plans. We will apply transformations to assure normality, run descriptive statistics, and assess potential covariates to include. While maximum effort will be made to retain all participants and minimize the amount of missing data, we anticipate there will be some data lost-to-follow-up and incomplete measures. Therefore, we will address missing data in the analysis plan by applying advanced statistical techniques, such as “multiple imputations” using PROC MI in SAS and IVEWARE SAS macro. Our overall approach will be to employ multivariate analysis to assess associations among key variables using the appropriate models based on the distribution of the data (i.e., normal, categorical data, count data, reaction time data). Since this is a cluster-randomized trial, adjusting the covariates (e.g., child sex, age, race/ethnicity) will aid in controlling additional unbalancesess due to the limited sample size. All analysis will be done using SAS 9.3 or R 4.1.0⁹⁶⁻⁹⁸. Additionally, we will perform “intent to treat”

analysis and assume all subjects comply to the assigned group. Findings/results from the study will also follow the CONSORT guidelines.

Power considerations. When we calculate the sample size and power, we assumed the intra-cluster correlation is 0.3. The achievable power is calculated for a detectable effect size, which is the detectable mean difference standardized by the square root of sample variance. Given the randomization design with 70 children in the intervention group and 50 children in the control group, we have 80% power to detect a difference in cognitive SR, behavioral SR, or emotional SR with an effect size of 0.52 and a Type I error level of 0.05.

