Specific analysis plan for Aim 1. Examine the immediate (pre- to post-test) intervention effects of CHAMP (compared to control participants) on cognitive SR (cognitive flexibility, working memory, attention shifting), behavioral SR (behavioral inhibition), and emotional SR (emotion regulation). The immediate post-intervention effect of CHAMP (compared to control participants) on each SR outcome variable will be evaluated at post-intervention. We will examine descriptive statistics for both pre-and post-intervention SR outcome variables for each group. The change in cognitive SR, behavioral SR, and emotional SR scores will be compared between the intervention (CHAMP) and control groups using regression models, adjusting for other confounding factors. We assume randomization will be successful and we will monitor throughout the trial. It is always good practice to monitor along the way and we will do so, but randomization may be imperfect as this is a randomized cluster trial taking place in the real world (i.e., Head Start setting). If randomization does not work this will lead to biased results and methodology, our planned analyses to adjust other variables will be considered. Random effects will be included in the model to accommodate for the potential within-cluster correlations due to nested classroom data. We anticipate that some children will have only partial adherence to the intervention (i.e., attend a subset of sessions), thus we will also conduct a dose-response analysis where dose corresponds to number of sessions. We will investigate the amount of attrition from pre-to post-intervention, and attempt to identify baseline (or pre-intervention) predictors of dropping out. The information will indicate possible bias in the change estimates.

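### The SAP's self-regulation power (80% at effect size 0.52) ignores its own ICC of 0.3; with 10 classrooms per arm the detectable effect is about 0.81-0.88 and power at 0.52 about 40%

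*SAP*

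**What the plan says.** The SAP's power paragraph for the self-regulation measures (Supplemental Award) says of the calculation that "we assumed the intra-cluster correlation is 0.3". It defines the effect size as "the detectable mean difference standardized by the square root of sample variance". For "70 children in the intervention group and 50 children in the control group" and "a Type I error level of 0.05", it concludes that "we have 80% power to detect a difference in cognitive SR, behavioral SR, or emotional SR with an effect size of 0.52". The paragraph gives no number of classrooms, class size, sidedness, loss to follow-up or variance explained by covariates.

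The SAP's Aim 1 plan for self-regulation states: "The change in cognitive SR, behavioral SR, and emotional SR scores will be compared" between arms, using regression with random effects for classroom.

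The protocol's Objective 2 supplies the class structure: 120 children "receiving CHAMP (n = 10 classrooms) or an active free-play/recess control condition (n = 10 classrooms"). Its own sample-size paragraph for Objective 2 claims 85% power with 98 children, naming neither an ICC nor an effect size, and adds: "To account for a total of a 16.5% loss at post-intervention, we will recruit 120 subjects (60 subjects per arm) at baseline".

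**The concern.** An ICC of 0.3 is large. With six children per classroom on average (120/20) it gives a design effect of 1 + 5 × 0.3 = 2.5, so the detectable effect should rise by a factor of about 1.6. The printed 0.52 shows no such rise: it is what one gets by treating all 120 children as independent.

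This is the SAP's only power statement for self-regulation, and it covers all three domains. A reader who trusts it would take a null result as good evidence against effects of about half a standard deviation. The planned mixed model will incur the clustering penalty that the power figure leaves out.

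**Working it through.** **Inputs.** From the SAP power paragraph: 70 and 50 children, ICC 0.3, Type I error 0.05, 80% power, effect size in SD units (SD = 1). From the protocol, Objective 2: 10 classrooms per arm and 16.5% loss. Assumed because the documents are silent: two-sided test, ICC of 0.3 on the variable analysed, equal class sizes within an arm, no variance reduction from covariates.

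**1. Reproduce 0.52.** For independent children:

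- SE = √(1/70 + 1/50) = 0.1852
- Detectable effect = (1.960 + 0.842) × 0.1852 = 0.519; with a t distribution on 118 df, 0.523
- Power at 0.52 = 80.2% (normal) or 79.5% (t)

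This is the SAP's figure, at ICC 0.

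**2. Apply ICC 0.3 with 10 + 10 classrooms.** Classes average 7 and 5 children. SE = √(DE₁/n₁ + DE₂/n₂), with DE = 1 + (m − 1) × ICC:

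- DE₁ = 1 + 6 × 0.3 = 2.8; DE₂ = 1 + 4 × 0.3 = 2.2
- SE = √(2.8/70 + 2.2/50) = √0.084 = 0.2898
- Detectable effect = 2.802 × 0.2898 = 0.812; with t on 20 − 2 = 18 df, 0.859
- Power at 0.52: Φ(0.52/0.2898 − 1.960) = Φ(−0.166) = 43%; with t, 40%

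A simulation of t tests on class means (40,000 runs) gave about 40% power at 0.52 and 80% at 0.86.

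**3. Add the protocol's 16.5% loss.** 70 × 0.835 = 58.45 and 50 × 0.835 = 41.75 children, or 5.845 and 4.175 per class:

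- SE = √(2.4535/58.45 + 1.9525/41.75) = 0.2979
- Detectable effect 0.835 (normal) or 0.883 (t); power at 0.52 is 42% or 38%

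**4. Look for a layout that gives 0.52.** ICC 0.3, no loss, 80% power:

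| Layout | Detectable effect, normal to t | Power at 0.52 |
|---|---|---|
| 10 + 10, 70/50 children | 0.81-0.86 | 43-40% |
| 10 + 10, 60/60 children | 0.81-0.86 | 44-40% |
| 12 + 8 | 0.82-0.87 | 42-39% |
| 15 + 15 | 0.71-0.73 | 54-51% |
| 35 + 25 (two children per class) | 0.59-0.60 | 69-68% |
| 10 + 10, one-sided | 0.72-0.75 | 56-53% |

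With 10 classrooms per arm, even unlimited children per class leaves SE = √(0.3/10 + 0.3/10) = 0.2449, a detectable effect of 0.69 two-sided or 0.61 one-sided (normal). The nearest match found is one-sided with two children per class (0.525), which needs 60 classrooms against the protocol's 20.

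**5. What ICC does 0.52 imply?** With 10 + 10 classrooms and the normal formula, about 0.001. An ICC of 0.005 gives 0.525 and 0.01 already gives 0.531. With t on 18 df even ICC 0 gives 0.549.

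**6. Could baseline adjustment explain it?** If adjustment multiplies the SE by √(1 − r²), reaching 0.52 before loss needs r = √(1 − (0.52/0.812)²) = 0.77, or 0.80 with t. At r = 0.5 the detectable effect is 0.812 × 0.866 = 0.70 to 0.859 × 0.866 = 0.74.

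**The case against.** Four points can be made for the plan.

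- **Class count.** The SAP paragraph gives none, so its inputs do not define a clustered calculation. The 10 + 10 comes from the protocol, whose sample-size text plans 60 per arm, whereas the SAP has 70 and 50; the class structure may have changed with the allocation. This stands as a caution about the exact replacement figure. It does not rescue 0.52, which no two-sided layout tried attains at ICC 0.3.
- **Definition of effect size.** If the sample variance in the SAP's definition already includes the design effect, 0.52 follows at any ICC. The text does not say so, and 0.52 would then equal about 0.52 × 0.812/0.519 = 0.81 ordinary SDs. A reader would still be misled.
- **Adjustment.** A strong baseline covariate could deliver 0.52, and the correlation needed depends on how it divides between child and class level. For example, 0.5 between children and 0.85 between classes also gives 0.52 by the normal formula. But neither document states any such correlation, and the SAP offers its covariates (sex, age, race/ethnicity) as a control for imbalance, without claiming a gain in precision.
- **Importance.** Self-regulation is a secondary aim, the project's main sample size rests on physical activity, and classroom random effects are already planned. This is fair: the correction concerns a statement, not the conduct or analysis of the trial.

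The like-for-like comparison with the SAP's 0.52, which mentions no loss, is 0.81-0.86; 0.83-0.88 also brings in the protocol's loss.

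**Conclusion.** The point holds. The SAP's 80% power at 0.52 is the result for 70 and 50 independent children and is inconsistent with the ICC of 0.3 stated beside it. With 10 classrooms per arm, two-sided 0.05, ICC 0.3 on the analysed variable and no covariate gain, the effect detectable with 80% power is about 1.6 times larger than stated before loss. Power at 0.52 is about half the stated value, with or without the 16.5% loss. The mismatch does not depend on the exact class count; the replacement figure does. What is wrong is the plan's account of what the trial could detect on self-regulation; the planned analysis stands.

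**What to change.** In the SAP's power paragraph for self-regulation, recompute at ICC 0.3 with the actual number of classrooms. If that is 10 per arm, say that 80% power is available for effects of about 0.83-0.88 after 16.5% loss (0.81-0.86 with no loss), or that power at 0.52 is about 40%.

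State the inputs now missing: classrooms per arm, sidedness, whether the ICC refers to scores or to change scores, any baseline adjustment with its assumed correlation, the loss assumed, and which SD standardizes the effect. If an adjustment or an inflated variance lay behind 0.52, give it and show the calculation.

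Use one allocation, 60/60 or 70/50, in both documents. The choice barely matters: 60/60 gives 0.81-0.86, or 0.83-0.88 after loss. Bring the protocol's Objective 2 statement (85% power with 98 children) into line by giving its effect size and ICC.

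The cost is a few sentences across the two documents and a less favourable figure for a secondary aim. No extra children are needed and the analysis does not change.

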Aim 2. Test the hypothesis that improved SR (*cognitive flexibility, working memory, behavioral inhibition, emotion regulation*) is associated with improved motor competence, perceived motor competence, and objectively-measured PA from pre- to post-test.

Impact. From an educational perspectives, positive findings will provide initial support for CHAMP as an effective intervention to enhance self-regulation and contribute to healthy growth and development in children at risk for obesity.

Clinical Trial Statement. Exploratory study to determine effect (immediate and sustainable) of a 3600 min motor skill intervention on motor competence, physical activity, and perceived competence in preschoolers.

C. Background

Developmental Perspective to Promote Sustainable Physical Activity. Ethnic-minorities and low income populations have an increased risk of cardiovascular disease and engage in less physical activity (PA).² Increasing levels of PA could help prevent cardiovascular disease.³ Thus, there is a need to identify effective approaches for promoting positive and sustainable PA in children that contribute to long-term cardiovascular health. Previous interventions aimed at promoting positive and sustainable PA levels in children have had limited success.¹⁴ A gap in prior PA intervention research is that long-term sustainability has not been addressed from a developmental perspective, nor has it addressed the impact of developing motor competence (MC) and perceived motor competence (PMC) on PA.^{14,15} The proposed project is significant in that it will address this gap in intervention research by examining the immediate (pre-post) and long-term (3 yr follow-up) influences of establishing a strong foundation of MC and PMC (\approx 3600 min dose) on PA levels from early through middle childhood.

It takes time for a young children to develop MC, which does not occur “naturally” or even when provided opportunities to be active,^{10,12,16,17} and PMC (i.e., perception of their movement capabilities).¹⁸ These processes are cumulative and are modified by growth and maturation processes that are constantly developing during the transition from early to middle childhood.¹⁹ Thus, the link between the development of MC and PMC is a critical aspect of the [name] et al.⁵ model (see Figure 1), which hypothesizes that building a strong foundation of MC in early childhood is a critical precursor for PA via the development of accurate PMC.

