The Children's Health Activity Motor Program (CHAMP) Implementation. CHAMP will be implemented during the scheduled movement sessions at each participating preschool (see preschool letters of support, Appendix A). CHAMP consists of (4, 30-minute classes a week or 3, 40-minute classes a week, based on the needs of the school schedule). ~~~30 weeks per year that will equate to ~3600 minutes of intervention time (30 min sessions X 4 days per week X 30 weeks per year)~~. Each session will consist of three parts: (a) 2 -3 min of motor skill introductory activity, (b) 25 min of motor skill instruction and practice, and (c) 2 -3 min motor skill closure activity. The control condition will be the preschools typical activity programs (i.e., outdoor/freeplay recess) and will be implemented according to the existing procedures within the preschool center. The centers outdoor program consist of outdoor free-play activity on a large playground area with a variety of play structures (swings, slides, ladders) that promote gross movement and activity in preschoolers. For the control condition, there will be no planned instruction nor activities provided by the classroom teachers. CHAMP will be implemented by two trained movement science specialists (1 instructor and 1 assistant). Instructors will attend a 3-day (4 hr/day) workshop/training session prior to the start of the intervention. The training workshops will be conducted by [name], an expert in movement/physical activity programming in early childhood settings and the developer of CHAMP. During the training workshops, instructors will learn the theoretical approach of CHAMP, see and actively participate in a CHAMP session and demonstrate effective implementation of the CHAMP intervention. During the training session, instructors must be able to provide a range of cues and prompts to promote skill learning, set up and demonstrate basic task progressions for motor skills, modify tasks based upon the child's present level of performance and rates of improvement, and implement CHAMP with fidelity, appropriate transitions and pacing, while ensuring safety. All training sessions will be digitally recorded and available through a private YouTube channel. A printed manual will also be provided to promote fidelity of the intervention. During the intervention, instructors will wear wireless microphones and digitally record each CHAMP session in order to determine fidelity. Ensuring fidelity demonstrates a measure for the internal validity of CHAMP.⁴⁴ Fidelity will be calculated from the digital recordings using a systematic observation tool established for mastery interventions.⁴⁵ CHAMP fidelity checks will be conducted during week 1, 3, 7, 15, and 25. [name] will deliver fidelity support (additional training) to instructors by providing adjustments to teacher behaviors if CHAMP specialists are not implementing CHAMP with fidelity. Concurrently, during weeks 1, 3, 7, 15 and 25, systematic observations tools at the control site will also occur for additional internal validity.⁴⁶

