
Data Collection. Trained graduate students external to the project (i.e., not involved in intervention delivery) will collect data using standardized instruments. In August (first month of the academic year), informed consent will be obtained and will be followed by the collection of pretest measures. Based on past experience with large sample data collections ^{10,11,12,13,16,47,48}, we estimate that four, 30 – 35 minute sessions are needed to complete the assessments (e.g., Height, Weight, MC, and PMC, Self -Regulation) for each class and a fifth day will be used for any absences (i.e., make-ups). Physical activity will be measured using accelerometry (ActiGraph) for 7 days to capture the children's engagement during the weekday and weekend. A minimum of 3 weekday and 1 weekend day will be required for data analyses. Accelerometers will be calibrated with individualized measures (i.e., height, weight, sex, and age) collected at pretest. Data collection for both testing periods in year 1 (see project timeline, Table 2) will take a maximum of 6 weeks, which will allow for the 30 weeks of intervention to be implemented. Following initial data collection, physical activity participation and CHAMP will commence. Follow-up assessments will occur at the conclusion of the CHAMP intervention (post-test) end of Year 1 to examine the immediate effect of CHAMP on MC, PMC, and PA. Additional follow-up assessments will be completed to examine the sustainability effect of CHAMP during Year 2 – 4 (Spring of Year 2, 3, and 4).

Data collection in the elementary schools following the preschool intervention year will be facilitated in the same manner as preschool sites. The preschool centers are affiliated with specific elementary schools and are on the campus of the elementary schools. Permission for the project has been provided by the Superintendent, Center Directors, and Principals (see letters of support) of the elementary schools as well. Based on previous longitudinal work³² expected attrition due to relocation issues and/or disinterest in continuing the study will be 30% over 3 years. Thus, our initial oversampling will be 30%. To promote

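### The self-regulation dose-response analysis counts sessions without saying which class schedule the children had; if the 30- and 40-minute schedules were mixed, the session count would not measure time received

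*SAP*

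**What the plan says.** **Dose definition.** In the SAP's self-regulation supplement (specific analysis plan for Aim 1), the analysis is motivated by the expectation that "some children will have only partial adherence to the intervention (i.e., attend a subset of sessions". The exposure is set by the phrase "dose-response analysis where dose corresponds to number of sessions". The protocol's statistical section for Objective 2, Aim 1 uses the same definition. Neither place converts sessions to minutes or to percent attended, and neither names a schedule term.

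**Delivery.** The protocol (Objective 1, the intervention-approach section and CHAMP Implementation) allows "4, 30-minute classes a week or 3, 40-minute classes a week, based on the needs of the school schedule". Beside this wording stands struck-out text giving a single schedule of 30 minutes on 4 days a week. The Clinical Trial Statement describes the intervention by time, as a "3600 min motor skill intervention". The Data Collection section sets the duration at 30 weeks.

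**Session content.** CHAMP Implementation lists the parts of each session, including "b) 25 min of motor skill instruction and practice", directly after allowing both schedules. The intervention-approach section ties the same breakdown to a 30-minute session. No breakdown is given for 40 minutes.

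**Cohorts.** The protocol is titled as the Cohort 2 plan. It states that Cohort 2 takes no part in Objective 2 and excludes that cohort from each self-regulation measure. The SAP gives no session length or weekly frequency.

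**The concern.** Session count stands in for time received only when every session has the same length. If some classes had four 30-minute sessions and others three 40-minute sessions, a fully adherent child on the second schedule would carry the same dose value as a child who attended three quarters of the first. Because the school timetable decides the schedule, the exposure would also carry a class- or school-level characteristic unrelated to adherence. One pooled slope per session would then describe two different exposures, and the answer to the partial-adherence question would be attenuated and harder to interpret.

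**Working it through.** **Inputs from the documents:** 4 × 30 or 3 × 40 minutes a week (protocol, CHAMP Implementation); 30 weeks (Data Collection); 3600 minutes in total (Clinical Trial Statement); 10 CHAMP classrooms (protocol, Objective 2); 70 intervention children and intra-cluster correlation 0.3 (SAP supplement, power considerations).

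**Step 1: reproduce the stated dose.** Minutes = sessions per week × length × weeks.
- 4 × 30 × 30 = 3600 minutes in 4 × 30 = 120 sessions.
- 3 × 40 × 30 = 3600 minutes in 3 × 30 = 90 sessions.

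Both match the protocol's figure.

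**Step 2: what a session count does under mixed schedules.**
- Equal scheduled minutes: 120/90 − 1 = 33% more sessions on 4 × 30, or 1 − 90/120 = 25% fewer on 3 × 40.
- Equal session count of 90: 90 × 30 = 2700 minutes against 90 × 40 = 3600 minutes.

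**Step 3: single schedule.** Minutes = constant × sessions, so r² = 1 and nothing is lost.

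**Step 4: mixed schedules with no class term (simulation).** Assumptions: half the children on each schedule; attendance normal with mean 80%, truncated to 0–100%. The r² between sessions and scheduled minutes is 0.42, 0.59 and 0.70 for attendance SDs of 10, 15 and 20 percentage points.

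**Step 5: mixed schedules with a classroom random intercept (simulation).** The attendance assumptions are those of step 4. There are 10 classes of 70/10 = 7 children, 5 classes per schedule, and intra-cluster correlation 0.3. The outcome is driven by scheduled minutes at an assumed 0.5 SD per 600 minutes, and the session slope is rescaled at 35 minutes per session, the midpoint of 30 and 40.

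| Attendance SD (points) | Slope kept, no class term | Slope kept, class random intercept | Information lost, class random intercept |
|---|---|---|---|
| 10 | 41% | 71% | about 32% |
| 15 | 59% | 84% | about 20% |
| 20 | 68% | 88% | about 16% |

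Information is the squared z-ratio. Separate runs of this set-up agree on the slope: 71–74%, 82–84% and 88–89% kept. The lowest and highest of these give the attenuation range of 100 − 89 = 11% to 100 − 71 = 29%. The information figures are rougher. A repeat gave losses of 35%, 22% and 14% from the spread of slopes across simulated trials, and 25%, 14% and 10% from model standard errors.

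**Step 6: is the dose really equal?** Only in scheduled minutes. If 25 practice minutes apply to every session whatever its length, weekly practice is 4 × 25 = 100 against 3 × 25 = 75 minutes, and session count would track that correctly.

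**The case against.** The strongest objection is that the problem may not exist among the children analysed. The two-schedule wording is in the Cohort 2 plan, Cohort 2 gives no self-regulation data, and the struck-out text shows that a single schedule was once written. This stands, and it makes the point conditional. It does not remove it. The same protocol carries the Objective 2 analysis, describes all 300 children, and nowhere states which schedule the self-regulation cohort had.

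A second objection is that the plan asks about children who attend only some sessions, and a session count answers that directly. This is fair when there is one schedule. With two, the same count means different proportions attended.

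A third is that classroom random effects absorb much of the schedule difference, since sessions and minutes are proportional within a class. This also stands and is built into step 5. It assumes that the random effects named for the main model carry over to the dose-response model, which the SAP does not say explicitly.

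Some stronger readings are tempting but not supported:
- A reader might infer that equal doses are coded as 33% apart in this analysis. That needs mixed schedules in the self-regulation cohort, which the documents do not establish.
- A reader might take 1 − r² from step 4 and conclude that 30–58% of the dose information is lost. That ignores the planned classroom random effects.
- A reader might conclude that minutes are plainly the right exposure. The session-content text leaves practice time in a 40-minute session undefined.

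**Conclusion.** The definition is incomplete, and the consequence is conditional. If the self-regulation cohort had one schedule, the loss is 0%. If it was split evenly, and classroom random effects are used as assumed in step 5, the slope is attenuated by roughly 11–29% and about 16–32% of the information is lost, the larger figures applying when attendance varies least. The split, the attendance distribution and an outcome driven by scheduled minutes are all assumptions; none is in the documents. The analysis is supplementary, and the intention-to-treat comparison of randomised groups does not use session counts, so it is unaffected. Severity is minor.

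**What to change.** In the SAP's self-regulation supplement:
1. State which schedule(s) the self-regulation cohort received.
2. Define dose as scheduled minutes attended (sessions attended × scheduled session length) or as percent of scheduled minutes; alternatively, keep sessions and adjust for schedule.
3. State that the classroom random effects apply to the dose-response model.

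In the protocol, reconcile the session-content description in the intervention-approach and CHAMP Implementation sections with the 40-minute option, so that a minute of dose means the same thing in every class. No change to delivery is proposed.

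The cost is a short SAP edit and one derived variable from attendance records and the timetable. If only one schedule was used, scheduled minutes are a constant multiple of sessions and the result is unchanged apart from its units.
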